## **7. Risks and Discomforts**

All procedures in this study are minimal risk. The risks and discomforts described below are all expected.

#### Vision Tests

There are no expected risks or discomforts associated with the brief vision tests in this study. These tests are non-invasive and non-contact, requiring only that the subject read aloud what they view on a computer screen or indicate when they see a target.

#### Driving Simulator

During testing using the driving simulator, there is little risk to the patient's health and safety, apart from the possibility that they experience "simulator sickness." Simulator sickness is similar to motion sickness and is felt by some people when moving in a simulated environment. The effects can range from slight to severe; most individuals will feel little to no effect. Typically, about 25% of participants experience mild simulator discomfort.

In setting up the simulator environment we have made every effort to reduce the likelihood of simulator sickness. The room is air conditioned (reasonably cool climates have also been shown to be helpful in minimizing the likelihood of simulator sickness). There will also be cool water and crackers on hand. Subjects will be introduced to the simulator environment through a graduated training drive that introduces the subject to the simulator environment in such a way as to minimize the likelihood of simulator sickness. During acclimatization and practice drives, the subject will be instructed to handle turns slowly and not overcorrect steering maneuvers (which can contribute to feelings of simulator sickness). There will be programmed breaks in testing sessions, which will help to reduce the risk of simulator sickness, and subjects will be able to take a break or stop at any time without consequence. In addition, the researcher will ask the subject for their physical comfort after each simulated drive and will offer a break or will terminate the session if necessary.

If any participant experiences simulator discomfort to an extent that the driving simulator session has to be terminated, an expected adverse event form will be completed.

Videos recorded during the driving sessions will be taken from behind the driver's seat so the participant's face will not appear in the recordings.

#### Confidentiality

Procedures to minimize risks to confidentiality include recording demographic and contact information on a separate form from the rest of the experimental data, storing in locked file cabinets all forms or records with information about a subject that would allow identification, and the use of unique subject identifier codes on all experimental research data forms and electronic data files. Any electronic data files that would allow subject identification are password protected on a secure server.

### **8. Benefits**

**Potential Benefits to Participants:** Subjects' scanning behaviors may improve following the training.

**Potential Benefits to Society:** The knowledge gained may lead to the development of improved rehabilitation training for drivers with HVFL, which may improve driving safety.

### **9. Statistical Analysis**

This is an open-label clinical trial to provide data for a future controlled randomized clinical trial. The target sample size to complete the study is 16 participants, based on prior and pilot data showing large cue-related improvements in blind-side scanning (Cohen's  $d \approx 0.8$ ), including metrics analogous to the primary outcome for this clinical trial, providing ~80% power for within-subject comparisons (paired t-test,  $\alpha = 0.05$ ). The primary analysis will be a within-subjects comparison of (1) the proportion of intersections with an early large blind-side scan and (2) the proportion of detected hazards approaching from the blind side, pre- versus post-training. Secondary analyses will also be within-subjects comparisons of other scanning behaviors (including the number, direction, and magnitudes of scans) and responses to hazards (such as time to respond to the hazard) pre- and post-training. Analyses will use mixed-effects models (GLMMs for binary, LMMs for continuous) with session as a fixed effect and participant/intersection as random intercepts, assuming model assumptions are met.

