**Table 1: Schedule of visits and assessments**

	Visit 1	Visit 2	Visit 3	Visit 4	Visit 5	Visit 6	Visit 7
Informed Consent	X						
Visual acuity	X						
Visual fields	X						
Contrast sensitivity	X						
Neglect tests	X						
Cognitive status test	X						
Ocular, driving and other relevant history	X						
Driving performance evaluation	X				X	X	X
Reminder cue training		X	X	X			

Driving simulator

The simulator (at Schepens Eye Research Institute) comprises multiple screens, an adjustable driver's seat, steering wheel, accelerator, and brake pedals. Participants will drive along predetermined routes in the virtual world guided by audio cues simulating GPS navigation. There will be other traffic on the road and the routes will include a variety of maneuvers in a city environment. Hazards (such as pedestrians and other vehicles) will be programmed to appear in various situations in some of the drives.

Participants will be instructed to obey all normal rules of the road, avoiding collisions, and maintaining a speed near the posted speed limit.

After acclimatization and practice drives in the driving simulator, each participant will complete evaluation drives (about 10 minutes each) at Visits 1 and 5- 7 without scanning reminder cues and training drives (about 6 minutes each) with reminder cues at Visits 2-4. Head and eye movements of the driver will be recorded using a remote camera-based tracker mounted in the simulator. In addition, a video camera placed behind the participant will be used to record the screens of the driving simulator to facilitate interpretation of driving behavior data automatically recorded by the simulator. Rest breaks will be scheduled into testing sessions and subjects will be able to take a break or stop at any time, without consequence.

Plans for return of research results

There are no plans to return research results to subjects at the end of the study. If subjects indicate an interest in the outcome of the study, a note-to-file will be made, and the PI may share the final published manuscript with these study participants.

Primary and secondary outcomes

- **Primary outcome measure:** Our primary outcome measure will be the proportion of intersections at which participants make an early large scan to the blind side (side of the field loss) and the proportion of detected hazards approaching from the blind side, pre- versus post-training.

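### The trial is sized on a paired t-test of participant-level change, but the stated mixed model has random intercepts only, so it ignores differences between participants in the training effect and does not target the change in proportion

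*Combined protocol and SAP*

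**What the plan says.** Section 6 (Primary and secondary outcomes) defines two primary outcomes, both proportions compared before and after training. The first reads: "Our primary outcome measure will be the proportion of intersections at which participants make an early large scan to the blind side". The second is the proportion of blind-side hazards detected.

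Section 9 gives the purpose: "This is an open-label clinical trial to provide data for a future controlled randomized clinical trial". On size it says "The target sample size to complete the study is 16 participants", rests this on earlier data "showing large cue-related improvements in blind-side scanning" with d about 0.8, and describes the result as "providing ~80% power for within-subject comparisons (paired t-test", alpha 0.05). It frames the primary analysis as a within-subject comparison of the two proportions, and then gives the model: "Analyses will use mixed-effects models (GLMMs for binary, LMMs for continuous) with session as a fixed effect and participant/intersection as random intercepts", provided that model assumptions hold.

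Section 9 does not state a link function, the effect measure to be reported, a confidence interval for the change in proportion, the SD or correlation of participant-level change, or a fallback if assumptions fail. The number of intersections or hazards per evaluation is not given anywhere.

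**The concern.** The sizing and the model describe different analyses. A paired t-test takes one difference per participant and judges the mean difference against its spread between participants. A GLMM with random intercepts only lets participants differ in overall level but gives everyone the same session effect. The spread of training effects between people, which is the error term of the paired t-test, has no place in it. Any such spread is ignored when the standard error of the session effect is formed.

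Two things are at stake. The first is validity: standard errors come out too small if people respond differently to training. The second is usefulness for the later trial: neither a change on the proportion scale nor its SD is named as an output, although supplying data for that trial is the stated purpose.

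**Working it through.** **1. The plan's own figure.** Inputs from Section 9: n = 16, d = 0.8, alpha = 0.05. Assumed: two-sided test, and d read as mean change divided by SD of change. The noncentrality is 0.8 × √16 = 3.2 on 15 df, and the critical t is 2.131. Exact power is 84.8% (82.1% at n = 15, 79.0% at n = 14). So 16 is adequate for the paired t-test. That power belongs to participant-level differences, not to the session coefficient of a GLMM.

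**2. What the random-intercept model leaves out.** Let m be the number of intersections per session, v the average of p(1 − p), and τ the SD between participants of the training effect in logits.

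- Variance of one participant's log-odds change as the stated model sees it: about 2/(m·v).
- Actual variance: about 2/(m·v) + τ².
- Ratio: R = 1 + τ²·m·v/2.
- Approximate type I error of a nominal 5% test: 2Φ(−1.96/√R).

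Assumptions: participant intercepts with SD 1 logit centred at 50%, so v ≈ 0.207 (numerical integration); m = 12 or 24; τ = 0.5 or 1. For scale, a 0.5-logit effect moves a participant from 50% to 1/(1 + e^−0.5) = 62%.

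| m | τ | 2/(m·v) | R | 1.96/√R | Type I, formula | Type I, simulated model | Type I, simulated paired t |
|---|---|---|---|---|---|---|---|
| 12 | 0 | 0.81 | 1.00 | 1.96 | 5% | 4.0% | 5.6% |
| 12 | 0.5 | 0.81 | 1.31 | 1.71 | 9% | 8.6% | 4.8% |
| 12 | 1 | 0.81 | 2.24 | 1.31 | 19% | 16.0% | 5.6% |
| 24 | 0 | 0.40 | 1.00 | 1.96 | 5% | 3.8% | 3.8% |
| 24 | 0.5 | 0.40 | 1.62 | 1.54 | 12% | 16.8% | 6.0% |
| 24 | 1 | 0.40 | 3.48 | 1.05 | 29% | 26.8% | 4.2% |

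The simulated columns use N = 16, 500 replicates per cell, a logit link, a likelihood-ratio test and no intersection effect. Pre and post logits are u − s/2 and u + s/2, so the null is true on both the logit and the proportion scale. The Monte Carlo standard error at 12% is √(0.12 × 0.88/500) = 1.5 points. A second simulation with the same N and intersection counts gave 9-13% at τ = 0.5, 17-26% at τ = 1, and 3-6% for the paired t-test. The 16.8% cell lies above both the formula and that second result, so I quote the lower range.

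Two features follow from the formula. N does not appear in R, so recruiting more participants would not remove the inflation. R grows with m, so it is smaller for an outcome with few events per session, as may be the case for hazards.

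**3. The session coefficient does not fix the quantities of interest.** Take a conditional log-odds ratio of 1.0, a conditional baseline of 50% and no variation in effect. The change in proportion is then 22.1 points at participant-intercept SD 0.5, 19.7 at SD 1 and 14.8 at SD 2. Over a wider set of assumptions (baseline 30% to 70%, intercept SD 0.5 to 2, τ = 0 or 1, 10 to 40 intersections per session), the same log-odds ratio of 1.0 goes with a change in proportion of 0.12 to 0.23, an SD of participant-level change of 0.10 to 0.29, and a paired d of 0.52 to 2.12. An assumed d of 0.8 therefore cannot be checked from that coefficient.

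**The case against.** An intersection-level GLMM is a standard analysis of repeated binary data, it can allow for differences between intersections, and sizing a small pilot on a simpler test than the final model is common. That stands. The objection here is to the missing random session effect, not to mixed models.

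Section 9 does call the primary analysis a comparison of proportions, and every participant's pre and post proportions will be on file. A reader might infer that the plan cannot yield the change in proportion or its SD. The documents do not support that: both can be computed from the collected data, and the plan is silent on them without excluding them. A reader might also infer that the later trial will be undersized because an odds ratio overstates the change. That would require a logit link, back-transformation at zero random effects, large variance components, a mid-scale baseline, and a later trial sized on the result. The documents establish none of these.

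Nor is the power statement an error worth correcting. With both d and power given as approximate, 84.8% against about 80% is rounding on the safe side.

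Variation in the effect is not proven either. Section 1 reports that weaker scanners improved more, but this was in drives with against without cues, and weaker scanners have more room to improve on the proportion scale even if the logit effect is constant. It makes variation plausible and no more. With none, the stated model holds its level (about 4% simulated).

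**Conclusion.** The point holds. The stated model assumes one training effect for all participants, while the sample size rests on an analysis that does not. If the effect varies with SD 0.5 to 1 logit between people, a nominal 5% test has a real error rate of about 9-13% to 17-26%, with confidence intervals too narrow to match; the paired t-test stays at about 3-6%. These sizes rest on assumed intersection counts, intercept SD, effect SD and link, because the documents give none of them.

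Reading the participant/intersection notation as crossed or as nested changes nothing here: neither reading supplies a participant-by-session term. Separately, the primary estimate is not pinned to the scale of the defined outcome, so two analysts could follow Section 9 and report different primary results. This should be changed before analysis. It does not call the design or the sample size into question.

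**What to change.** In Section 9:

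1. For each primary outcome, make the primary estimate the mean over participants of the post-minus-pre difference in proportion, with a t-based 95% CI. With 16 completers this has 15 df and half-width 2.131 × SD/√16 = 0.53 × SD of change. It is the analysis that the sample size assumes.
2. If the GLMM is kept, name the link, add a random session effect by participant, and report the difference in proportions averaged over the random effects with a participant-level bootstrap CI.
3. Report the SD of participant-level change and the pre-post correlation for each primary outcome, as inputs to the future trial.
4. State the number of intersections and blind-side hazards per evaluation.

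The cost is a few sentences and a few lines of code, with no new data, visits or participants. The downsides are that intervals will usually be wider than from the stated model, and that the participant-level analysis does not model differences between intersections. The GLMM with a random session effect can serve as a supporting analysis for the latter.

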#### 1. Background and Significance

Homonymous visual field loss (HVFL) affects the same side (left or right) of the visual field in each eye. HVFL results from post-chiasmal damage to the visual pathways and is contralateral to the side of the brain injury. The most common cause is stroke followed by traumatic brain injury, tumors, and brain surgery. In the United States, people with homonymous hemianopia (the loss of one half of the visual field) are permitted to drive in states where they meet the visual requirements for either a regular or a restricted license. For instance, they can drive in New Hampshire, Colorado and California where there are no minimum field requirements. People with homonymous quadrantanopia (the loss of one quarter of the visual field) are permitted to drive in most states because their field loss only affects one quadrant rather than a complete hemifield (as in hemianopia).

Drivers with HVFL could compensate for their vision loss by scanning toward the blind side of the visual field using eye and head movements. However, prior research suggests that drivers with HVFL sometimes fail to scan to the blind side when approaching an intersection or do not scan far enough resulting in impaired responses to hazards. A large gaze scan, up to 90°, composed of head as well as eye movements, may be needed to see hazards approaching from the blind side at a four-way intersection. People with HVFL do not have any stimuli from peripheral vision as to when to scan to the blind side (because they do not have any peripheral vision on that side). Therefore, they may be unaware that they have failed to scan to the blind side unless there is some consequence (e.g., a near crash, or another driver honks at them)

In a prior proof-of-concept driving simulator study, we evaluated auditory reminder cues as a method to alert individuals with HVFL when they failed to make a large scan to the blind side on approach to an intersection. We found that the reminder cues promoted a more proactive style of scanning, i.e., participants were more likely to make an early large scan in drives with than without the reminders, and participants who scanned less well showed greater improvement than participants who scanned well without the reminders. Moreover, when participants made an early large blind side scan, response times were significantly faster than when they did not make an early scan. These results

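### The primary mixed model has random intercepts only, so its standard error will be too small if the pre/post change varies between the 16 participants

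*Combined protocol and SAP*

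**What the plan says.** Everything on this point is in Section 9 (Statistical Analysis).

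- **Sizing.** "The target sample size to complete the study is 16 participants", at Cohen's d of about 0.8 and alpha 0.05, "providing ~80% power for within-subject comparisons (paired t-test").
- **Primary contrast.** "The primary analysis will be a within-subjects comparison of (1) the proportion of intersections with an early large blind-side scan", together with the proportion of blind-side hazards detected, before versus after training.
- **Model.** "Analyses will use mixed-effects models (GLMMs for binary, LMMs for continuous"), with "session as a fixed effect and participant/intersection as random intercepts".

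The section makes the models conditional on their assumptions being met, but names no check and no fallback. No random slope for session, participant-by-session term, robust variance or small-sample degrees of freedom appears anywhere in the document.

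On repeated observations, the driving simulator text in Section 6 says that "each participant will complete evaluation drives (about 10 minutes each) at Visits 1 and 5- 7 without scanning reminder cues". It gives neither the number of drives nor the number of intersections per session.

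On differences in response, Section 1 reports from the earlier simulator study that "participants who scanned less well showed greater improvement than participants who scanned well without the reminders".

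**The concern.** Session is a within-participant contrast, and each participant contributes many intersections per session. An intersection intercept and a binary model imply one data row per intersection. With intercepts only, the session effect is then tested against intersection-level noise. Adding intersections keeps shrinking the standard error, although there are still only 16 people whose change is being averaged.

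The sample size rests on a different error term. The error term of a paired t-test is the between-participant SD of the change, which the planned model sets to zero beyond binomial noise. That mismatch needs no assumption; it follows from reading Section 9.

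If the variation is not zero, the confidence interval for the primary result is too narrow. This is a single-arm study with no control group against which to judge a chance finding, and its stated purpose is to inform a later controlled trial.

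**Working it through.** **1. The plan's own figure.** For a paired t-test with n = 16, d = 0.8 and two-sided alpha 0.05 (sidedness is not stated), use the noncentral t with n - 1 = 15 df and noncentrality 0.8 × √16 = 3.2. Power is 84.8%. Power is 79.0% at n = 14 and 82.1% at n = 15, so 15 participants reach 80%. Sixteen is consistent with the plan and slightly conservative.

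**2. Size of the missing term, by formula.** Let m be the number of intersections per session and τ the between-participant SD of the session effect in logits. Both are assumed.

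- Noise variance of one participant's change: v = 2/(m × 0.21), where 0.21 is an assumed average of p(1-p).
- True variance: v + τ². A model without the slope sees only v.
- Standard-error inflation: k = √(1 + τ²/v). Type I error: 2 × [1 - Φ(1.96/k)].

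Example with m = 20 and τ = 1: v = 2/4.2 = 0.476, k = √(1 + 2.1) = 1.76, error about 27%.

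**3. Simulation.** There were 16 participants, two sessions, participant intercept SD 1 logit and true mean effect zero. The model was a random-intercept logistic GLMM (25-point Gauss-Hermite maximum likelihood, Wald z test), with 1,000 runs per cell. Intersection intercepts were left out for simplicity.

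| m | τ | Model SE / true SE | Type I error, GLMM | Type I error, paired t-test |
|---|---|---|---|---|
| 10 | 0 | 1.00 | 4.5% | 4.4% |
| 10 | 0.5 | 0.87 | 8.5% | 5.1% |
| 10 | 1.0 | 0.73 | 15.7% | 3.8% |
| 20 | 0 | 1.00 | 5.4% | 4.7% |
| 20 | 0.5 | 0.84 | 9.6% | 4.5% |
| 20 | 1.0 | 0.60 | 24.3% | 4.8% |
| 40 | 0 | 0.97 | 6.0% | 6.0% |
| 40 | 0.5 | 0.70 | 15.5% | 5.1% |
| 40 | 1.0 | 0.46 | 36.2% | 5.4% |

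A second set of runs with 15, 20 and 30 intersections (500 to 1,000 per cell) gave 4.6-7.4% at τ = 0, 9.2-16.8% at τ = 0.5 and 17-30% at τ = 1.0.

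**4. Cross-check from d = 0.8.** If d is standardised by the SD of change, that SD is the mean gain divided by 0.8. Binomial noise at 50% has variance 2 × 0.25/m. The ratio of the two shows how far the model variance falls short. Gain and m are assumed.

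| Gain | m | Ratio | Type I error |
|---|---|---|---|
| 10 points | 30 | 0.125²/0.01667 = 0.94 | 4% |
| 15 points | 15 | 0.1875²/0.03333 = 1.05 | 6% |
| 15 points | 30 | 0.1875²/0.01667 = 2.1 | 18% |
| 20 points | 15 | 0.25²/0.03333 = 1.88 | 15% |
| 20 points | 30 | 0.25²/0.01667 = 3.75 | 31% |

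**5. Small-sample reference.** Even with a slope in the model, a z reference is liberal with 16 participants: P(|t| > 1.96) on 15 df is 6.9%, or 7.7% with the maximum-likelihood variance.

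**The case against.** **The defect is conditional.** With τ = 0 the planned model holds its level, and the documents give no value for τ. This stands. On the other side, variation need not come from the training itself. A session-to-session SD of 0.35 logit (0.25 × 0.35, about 9 points at 50%) gives an SD of change of √2 × 0.35 = 0.5, the milder case above. Section 4 admits both hemianopia and quadrantanopia. Neglect and cognitive status are measured but are not exclusions. The cue may be auditory or tactile.

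**The Section 1 evidence is indirect.** It compares drives with and without cues, whereas the evaluation drives here have none. It may also be partly a ceiling effect: a common shift of 1 logit moves 50% to 73% (+23 points) but 90% to only 96% (+6), with no slope variance at all. This stands; the passage makes variation plausible but does not measure it.

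**The data might be aggregated.** With one proportion per participant and session, a random-intercept LMM on two sessions equals the paired t-test and the problem disappears. That is correct, but a binary GLMM with an intersection intercept points to intersection-level rows.

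**The simulation is not exactly the planned model**, because it has no intersection intercepts. This stands as a limit on the figures. Those intercepts would not supply the missing participant-by-session term.

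**Nesting.** A reader might infer from the slash that intersections are wrongly nested in participants. The slash may simply mean both. The document says that routes are set in advance, but not that every participant meets the same intersections. The notation needs clarifying; it is not a demonstrated error.

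**It is a pilot.** No confirmatory claim follows, and whether the later trial would be sized from this standard error is conjecture. But Section 2 does state a hypothesis to be tested, so a valid test is wanted.

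**Conclusion.** The point holds in conditional form. The planned model assumes the same pre/post change, on the model scale, in every participant. If that is false, the standard error is too small: 0.87 down to 0.46 of its true value over the assumed range. Type I error is then about 8-17% at a slope SD of 0.5 logit and about 16-36% at 1.0, against about 5% when there is no variation. The excess grows with the number of intersections per session. Slope SD, intersection count and intercept SD are all assumptions. A paired analysis of participant proportions stayed at 3.8-6.0% in every tabulated cell.

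A reader might go further and conclude that the standard error is certainly too small, or that the variance is understated nearly fourfold. The documents support neither. The ratio of 3.75 needs a 20-point gain and 30 intersections, and it falls to about 0.9 with a 10-point gain. The check also requires d to be standardised by the SD of change, which the document does not say. Nor do these calculations show that a few strong responders would drive the result.

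The mismatch between the sizing test and the analysis model stands without any assumption. I would class this as should-fix.

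**What to change.** Amend the model sentence in Section 9 to cover these points:

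- **Random effects.** Add a by-participant random slope for session to both the GLMMs and the LMMs. State whether the participant and intersection intercepts are crossed or nested: crossed if participants meet the same intersections.
- **Reference distribution.** Use Kenward-Roger or Satterthwaite degrees of freedom for LMMs. For GLMMs, which carry the binary primary outcomes, use a parametric bootstrap or a t reference with (completers minus 1) df.
- **Primary test.** Pre-specify the paired t-test on participant-level change in proportions, with (completers minus 1) df, as the primary test. At the least, make it the fallback when the slope model is singular or does not converge. Naming it as primary is cleaner, because switching tests on convergence depends on the data. It is also the test behind the sample size.

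The change is to wording only. Confidence intervals will be wider where participants differ in their change. The sizing claim is unaffected: the paired t-test has 84.8% power at n = 16 and d = 0.8, provided that d is standardised by the SD of change.
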